Unanticipated Problems. In general, unanticipated problems include any incident, experience, or outcome that meets **all** of the following criteria:

- 1) **unexpected** (in terms of nature, severity, or frequency) given (a) the research procedures that are described in the protocol-related documents, such as the IRB-approved research protocol and informed consent document; and (b) the characteristics of the subject population being studied;
- 2) **related or possibly related** to participation in the research (in this guidance document, *possibly related* means there is a reasonable possibility that the incident, experience, or outcome may have been caused by the procedures involved in the research); and
- 3) suggest that the research **places subjects or others at a greater risk of harm** (including physical, psychological, economic, or social harm) than was previously known or recognized.

AE and SAE Identification

The study population is known to experience a number of AEs and SAEs, as defined by OHRP that are not expected to be study-related. For instance, prior investigation by the research group with this population suggests that as many as 50% of subjects report "thoughts that they would be better off dead or of harming themselves in some way" over the course of the six months after their ED visit (See Appendix C for Participant Suicidality Safety Protocol). Overdose is also common in a population of

patients with risk for opioid use disorder and in previous work by [name] and others approximately 25% of patients in the HMC ED at high risk for opioid overdose had an overdose event (e.g. non-fatal or fatal) within 3 years. The study population often suffers from comorbid medical conditions pre-dating and possibly exacerbated by the ED visit and thus is likely to experience recurrent hospitalizations. Additionally, the study population is known to experience a high rate of incarceration.

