Given the high frequency of AE/SAE events in the study population, and having identified those SAEs/AEs that we anticipate to be study-related in the patient consent form, the study team has opted not to systematically assess for AEs or SAEs at each patient contact. However, the study team may become aware of AEs/SAEs through routine interactions with study subjects. Examples include while scheduling interviews or other patient contact, during baseline or follow-up interviews, intervention related activities, within the EMR, through a public records search (e.g., WA state death records), from public posts or private messages sent through the subject's social media (e.g., Facebook), or relayed by an alternate point of contact for the subject. Study team members will ensure that the PI and other relevant team members (e.g., research coordinator) are made aware of any relevant problems or SAEs via email, phone, or in-person within 24 hours.

SAEs/AEs that the study team becomes aware of through the course of conducting study procedures will be reviewed by the PI and study team to assess relatedness and expectedness will be classified by attribution, or an assessment of the relatedness to participation in the study protocol, with particular regard to the intervention. Specifically, they will be classified as one of the following:

- 1) **Not Related**
- 2) **Probably Related**
- 3) **Related**

AE/SAE and Unanticipated Problems Reporting

Study team members will report unanticipated problems on the Reportable New Information (RNI) form to the IRB, consistent with the UW IRB requirements. The UW IRB definition of Unanticipated Problem includes *a problem or event that meets all of the following criteria: unexpected, probably related to study, and places subjects at greater risk of harm*. Events meeting these criteria must be reported on a Reportable New Information (RNI) form to UW IRB within 10 business days. AEs/SAE's that are not unanticipated problems will not be reported. Additionally, [name] will notify the NIDA Project Officer of any unanticipated problems or significant human subject protection issues within 24 hours of discovery.

Anticipated AE/SAE

Anticipated AEs/SAEs will be tracked systematically and will be reviewed within 24 hours of discovery by the study PI to determine if it is an unanticipated problem. The following AEs/SAEs are anticipated in this study population and will be tracked systematically:

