- Suicidality including fatal suicide and non-fatal suicide attempt
- Overdose (fatal and non-fatal)
- Hospitalization
- Medication side effects

As mentioned above, the study team may become aware of one of these anticipated AEs/SAEs through a variety of means, which may include self-report by the subject while completing baseline or follow-up interviews, intervention related activities, relayed by an alternate point of contact for the subject, within their EMR or EDIE, through a public records search (e.g., WA state death records), or public posts or private messages sent through the subject's social media (e.g., Facebook). Any clinical questions about medications and possible/probable side effects will be triaged to the study PI ([name]) and her mentor, [name] (psychiatrist) to determine if it is related to the study and to make a determination about medication recommendations, reporting, and next steps. Anticipated AEs/SAEs will be systematically tracked using an Excel document to track the event and any comments related to this event. Specific actions around the event will also be documented if necessary. After the study PI is notified a decision will be made to determine if it is an unanticipated problem and this will be documented in the Anticipated AEs/SAEs log. See the Subject Suicidality Safety Protocol (see Appendix C) for details regarding how the study team will address subject suicidality during the conduct of the trial.

Other Patient Safety Reporting

Any other unanticipated problems, compliance issues, or safety concerns identified by the study team will be addressed within the study team including [name] and/or [name], and/or other study team members as appropriate, to assess severity and what steps, if any, are appropriate to take.

Protocol Deviations

The study team may determine the need to deviate from the approved study protocol. The team will make every effort to anticipate the need for protocol deviations and have these approved by the UW IRB prior to engaging in a change to procedures; however, the study team may be required to make deviations to eliminate hazards to patient safety without prior IRB approval.

The study team will document any known instances of non-compliance and report to the IRB per UW Human Subject Division policies per specifications in Table A.

Table A. Protocol Deviation or other Problems Reporting Requirements

Event Type	UW IRB Reporting

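### The protocol sets two different relatedness thresholds for an unanticipated problem, and its attribution scale has no place for a possibly related event

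*Protocol*

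**What the plan says.** All the relevant text is in Section V.A of the protocol, which introduces adverse events, serious adverse events and unanticipated problems as terms that follow the OHRP definitions.

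- **Unanticipated Problems.** Three criteria must all be met: the event is unexpected in nature, severity or frequency; it is "related or possibly related" to taking part; and it suggests greater risk of harm than was known. Possibly related "means there is a reasonable possibility that the incident, experience, or outcome may have been caused by the procedures involved in the research".
- **AE and SAE Identification.** The PI and study team review the events they learn of and assign an attribution. "Specifically, they will be classified as one of the following": Not Related, "Probably Related", or Related.
- **AE/SAE and Unanticipated Problems Reporting.** A second definition, attributed to the UW IRB, requires the event to be "unexpected, probably related to study, and places subjects at greater risk of harm". Events that meet it go on the RNI form within 10 business days. The section adds that "AEs/SAE's that are not unanticipated problems will not be reported". The NIDA Project Officer is to be told within 24 hours of any unanticipated problem, and also of any significant issue of participant protection.
- **Anticipated AE/SAE.** Suicidality, overdose, hospitalization and medication side effects are tracked in a log. The PI reviews each within 24 hours, "a decision will be made to determine if it is an unanticipated problem", and the result is logged.

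**The concern.** The general definition names possible relatedness and explains the term. The scale used to record attribution cannot express it, and the reporting definition sets a higher bar. The protocol does not say which definition prevails, or where on the scale an event belongs when causation is a reasonable possibility but not probable.

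Uncertain attribution is likely to arise here. The protocol describes a population with frequent hospitalization, overdose and other serious events unconnected with the study, and the intervention may include starting buprenorphine from the ED. Attribution is made by the PI and study team, and the PI also supervises the intervention. An explicit scale and a single threshold are worth more in that setting. At stake are the completeness of the safety record and whether an event that meets the protocol's own definition reaches the IRB or the funder.

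**Working it through.** There is no figure to reproduce and no arithmetic applies. The check sets the three relatedness rules side by side for each judgement that the team could reach.

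| Judgement on causation | Relatedness criterion, general definition | Relatedness criterion, UW IRB definition | Level on the attribution scale |
|---|---|---|---|
| No reasonable possibility | not met | not met | Not Related |
| Reasonable possibility, short of probable | **met** | **not met** | **none, and no placement rule** |
| Probable | met | met | Probably Related |
| Related | met | met | Related |

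The rules agree in three rows and part in one. The scale has the same cut-off as the UW IRB definition. The underlying conflict is therefore between the two definitions, and the missing level follows from it.

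Next, take an event in the second row that is also unexpected and suggests greater risk, and follow it through each route.

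1. *General definition.* All three criteria are met, so it is an unanticipated problem.
2. *Attribution.* One of three labels must be chosen and none fits. It could be placed down, as Not Related, or up, as Probably Related. The text does not decide.
3. *RNI form.* The UW IRB relatedness criterion is not met, so the form is not required. Under that definition the event is not an unanticipated problem, and the protocol says such events are not reported.
4. *Annual report to NIDA (Section IX).* This covers problems reported to the IRB, so an event that does not reach the IRB is not called for here either.
5. *24-hour NIDA notice.* This is required if the general definition applies. If the UW IRB definition applies, it is required only if the event counts as a significant participant-protection issue. The protocol does not say which definition is meant.
6. *Anticipated-event log.* If the event is one of the four listed kinds, it is logged and reviewed by the PI whatever its attribution label. The definition that the PI is to apply is again not stated.

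The same event can therefore be an unanticipated problem at step 1 and not one at step 3, with steps 5 and 6 undetermined.

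**The case against.** The strongest reply is that the scale does what it needs to do. The study commits itself to UW IRB procedures, the UW IRB threshold is probable relatedness, and the scale separates events at that threshold. The general definition reads like background text taken over from guidance. This accounts for the RNI form. It does not settle the matter, because Section V.A says that unanticipated problems are defined as OHRP defines them, and then gives that definition. The protocol also speaks of possible and probable side effects as distinct when it sends medication questions to the PI and psychiatrist, so the distinction is already in use.

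Three stronger readings are tempting, and the documents do not support them.

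- *Possibly related events must be recorded as Not Related.* The choice is forced but its direction is not. Downward placement is plausible because the reporting threshold is also probable relatedness, but that is an inference.
- *Such events drop out of review.* The four anticipated kinds are logged and reviewed by the PI whatever their label, questions about possible side effects go to the PI and psychiatrist, and safety reports are reviewed weekly.
- *Every possibly related event is misclassified.* The general definition defines unanticipated problems, not attribution, and relatedness is only one of its three criteria. Withdrawal after failed linkage is called a known risk under Pharmacotherapy in Section III.G, and overdose is described as common. Unless their severity or frequency is out of line, such events would ordinarily fail the unexpectedness and greater-risk criteria under either definition, and an added level would not make them reportable.

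It is also fair to say that the NIDA notice has a second, broader limb that depends on neither threshold. It could catch some of these events, but it leaves the first limb undefined.

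**Conclusion.** The inconsistency stands as a minor but safety-relevant point. Two definitions with different relatedness thresholds sit in one section, and the scale has neither a level nor a rule for the events that fall between them. An unexpected, possibly related event that suggests greater risk meets the protocol's own definition, may be recorded as Not Related, and need not be reported if the reporting paragraph is followed as written.

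The size cannot be stated. The documents give no rate of possibly related events, and only those that also meet the other two criteria are affected, so the number may well be small. No outcome or analysis in the SAP uses the attribution categories. The conclusion rests on reading the general definition as operative, which the opening of Section V.A supports, and on the absence of any placement rule elsewhere in the protocol.

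**What to change.** 1. Reconcile the two definitions in Section V.A, so that the text says which applies to which decision.
2. Add a Possibly Related level to the attribution scale and to the AE/SAE log, using the meaning that the protocol already gives the term.
3. State that the general definition governs the logged unanticipated-problem decision and the 24-hour NIDA notice, and that the UW IRB threshold decides only what goes on the RNI form.
4. Limit the sentence on events that are not reported to the RNI form, so that it does not override the NIDA notice.

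The cost is one added category and a few sentences. The downside is that a few more events may be reviewed or notified; how many cannot be derived from the documents. No treatment, visit or analysis changes.

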REDCap data quality will be monitored periodically by the study PI and/or data analyst. In the event that any changes need to be made to the data, these changes will be made directly in REDCap. There is a data logging tool in REDCap that allows administrators to track changes to the project. This tool provides access to an audit trail created by REDCap. For each entry that changes data in the database, REDCap records the date, time, username of the person logged in at that time, the type of event and the changes that were made. This audit trail in the data logging tool stores every entry/change throughout the life of the database. Specific checks for completion and accuracy are outlined below for the primary and secondary outcomes and for intervention and usual care activity. Certain patient-reported outcomes (PRO) will be used in the 'Anticipated AE/SAE' log as well. Specifically, PRO's on suicide and overdose will be reviewed as described above.

- Feasibility**

Feasibility measures include enrollment rates, retention rates at each outcome and followup assessment, intervention completion rates and number and types of contacts made by the interventionist. At team meetings, the CONSORT diagram will indicate enrollment and retention rates. At least monthly, the study RA/RC and PI will review the ED-LINC contact log in RedCap for completeness, accuracy and content. Feasibility of implementation will also be assessed using specific assessments of ED-LINC participants at the 6-month follow-up visit. The rates of completion of these assessments will be assessed.

- Substance Use and TLFB**

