The study team will document how many and what type of consults each patient in the usual care (UC) condition receives. This consultation information will be obtained primarily from the EMR and entered in to REDCap. The team will rely on information from the EMR to ensure completeness and accuracy of all UC documented in REDCap

VIII. INTERIM ANALYSIS PLANS

Interim analysis is not relevant as this is a pilot study and effect sizes are not being measured.

IX. CONTENT AND FREQUENCY OF DSM REPORTS TO NIDA

Annually, the PI ([name]) will submit a grant report (RPPR) to NIDA. The grant report is due in June every year and will include details on:

- Study progress which will include details on feasibility measures, secondary outcomes including substance use and health care utilization and any problems reported to the IRB. An enrollment table will be completed per NIH guidelines
- Responsible conduct of research training received

References

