Appendix C. ED-LINC PATIENT SAFETY SUICIDALITY PROTOCOL

This protocol addresses potential subject suicidal risk given that suicidal ideation is common among the patient population. Suicidal risk is indicated by subject self-report of suicidality or suicidal behavior. The following procedure addresses positive responses to the PHQ-9 or other reports of suicidality by study patients. Importantly, patients with a primary chief complaint of suicidal ideation or in the ED for treatment after a suicide attempt are not eligible for participation.

The study team collects patient-reported outcomes at baseline, prior to randomization, and at a series of post-randomization follow-up assessments according to a pre-determined schedule (1, 3, 6 months after the baseline assessment). These assessments include questions about patient psychological and emotional distress. Each assessment includes a question about having thoughts of self-harm or being better off dead on the Patient Health Questionnaire 9 item (PHQ-9) depression measure. The PHQ-9 question #9 asks patients “how often have you been bothered by thoughts that you would be better off dead or of hurting yourself in some way?” The response choices are: 0 = Not at all, 1 = A little of the time, 2 = More than half the time, 3 = Nearly all the time.

Work by Gregory Simon et al. (2013) in a general medical setting documented a low risk of completed and attempted suicide by subjects that endorsed a “1” on the PHQ-9 item #9 question; of those that responded with a “1”, approximately 1% attempted suicide and 0.08% completed suicide. The rates of attempts and completed suicide did increase with higher scores on the PHQ-9 item #9; however, the absolute risk remained relatively low; of those that endorsed a “3” on the PHQ-9 item #9, 4% attempted suicide over the course of a year. The low risk of suicide completion associated with a positive PHQ-9 led the study team to include a follow-up question to directly assess whether patients are currently having thoughts of suicide.

Suicidality or suicidal behavior discovered at baseline

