I. STUDY IDENTIFICATION INFORMATION

TITLE OF PROTOCOL: Emergency Department Longitudinal Integrated Care 2.0 (ED-LINC 2.0)

PRINCIPAL INVESTIGATOR: [name] MD MS

FUNDER OF PROTOCOL: National Institute of Drug Abuse (NIDA)

CLINICALTRIALS.GOV: A description of this clinical trial will be available on <http://www.clinicaltrials.gov>, as required by U.S. Law. **NCT03699085**

SAP Version date: September 2021

Table of Contents:

Summary of Clinical Trial Features.....	Page 3
Primary Outcome Measures.....	Page 4
Refusal Rates	
Follow-up Completion Rates	
ED-LINC Intervention and usual Care process Outcomes	
Implementation Appropriateness	
Satisfaction	
Perception of Care Coordination	
Secondary Outcome Measures.....	Page 5
Substance Use	

Summary of Clinical Trial Features:

The *Emergency Department Longitudinal Integrated Care* (ED-LINC) intervention is a stepped collaborative care model of care initiated from the ED for patients with OUD that combines evidence-based treatment elements, proactive care coordination and population-level outcome tracking. ED-LINC builds upon previous work by tailoring the collaborative care model for patients at high risk for OUD presenting to the ED. A central objective of ED-LINC is to provide evidence-based treatment for OUD and related co-morbidity while in the ED in conjunction with proactive longitudinal care coordination that links patients to ongoing treatment. Weekly caseload supervision with measurement-based care outcome tracking allows for the stepping up of care for patients with recalcitrant symptoms, as well as opportunities to oversee care management linkages to community services targeting the key outcomes of initiation of MOUD and retention in MOUD treatment.

The main objective of this study was to conduct a pilot pragmatic randomized clinical trial of ED-LINC (n=20) compared to usual care (n=20) for ED patients at a single-site at high risk for OUD. The primary outcomes of this study pertain to feasibility of the model, research strategy and implementation.

Primary Outcome Measures

All primary outcome measures used **descriptive statistics**

Refusal Rate was calculated as the number of patients that refused or declined the self-report screening procedure in the ED divided by the eligible number of patients that could have done the self-report screening during the enrollment period.

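### The SAP plans no by-arm summary of the harms the protocol tracks, and the protocol's rules for reporting those harms conflict

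*Protocol*

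**What the plan says.** **Collection.** Protocol Section V.A (Anticipated AE/SAE) lists suicidality, overdose, hospitalization and medication side effects. It states that "Anticipated AEs/SAEs will be systematically tracked using an Excel document to track the event and any comments related to this event". Three of the four also have a source that does not depend on arm:

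- Suicidality: Appendix C says of the PHQ-9 that "Each assessment includes a question about having thoughts of self-harm or being better off dead", with assessments at baseline and at 1, 3 and 6 months.
- Suicide and overdose self-report: Section VII.B.2 says that "PRO's on suicide and overdose will be reviewed as described above".
- Hospitalization: Section VII.B (Health Care Utilization) has EDIE inpatient visits pulled for every consented patient.

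Other adverse events are picked up as they come to notice, since "the study team has opted not to systematically assess for AEs or SAEs at each patient contact" (Section V.A, AE and SAE Identification).

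**Analysis.** The SAP states that "The primary outcomes of this study pertain to feasibility of the model, research strategy and implementation". It describes six such outcomes and one secondary outcome, substance use.

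**Reporting.** For unanticipated problems, Section V.A says: "Events meeting these criteria must be reported on a Reportable New Information (RNI) form to UW IRB within 10 business days". The next sentence reads "AEs/SAE's that are not unanticipated problems will not be reported". Section IX has the annual NIDA report cover feasibility and "secondary outcomes including substance use and health care utilization and any problems reported to the IRB". Appendix C has suicidality reported to a DSMB once it reaches the level of a serious adverse event.

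**The concern.** The events are collected, logged and judged one at a time, but no document says that they will be counted by arm. Section V.A defines an unanticipated problem partly by unexpected frequency. An excess in frequency shows only in aggregated counts, and an event already on the anticipated list will seldom qualify when judged singly.

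Section II.A says that the trial is meant to inform future studies of ED-LINC, and Section IV.C names the starting of medications such as naloxone or buprenorphine among the main study risks. If the SAP is followed as written, the final results would give retention, satisfaction and days of opioid use, with no count of overdoses, suicide attempts, deaths or admissions in either arm. Whoever designs the next trial would have neither a signal nor reassurance.

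**Working it through.** **Step 1. Trace each anticipated event through the documents.**

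| Event | Source common to both arms | Summary in SAP | Stated route out of the study team if not an unanticipated problem |
|---|---|---|---|
| Suicidality | PHQ-9 item 9 at four assessments; suicide self-report | None | DSMB, if at SAE level (Appendix C) |
| Overdose | Overdose self-report | None | None |
| Hospitalization | EDIE inpatient visits | None; utilization is absent | Annual NIDA report, as utilization (Section IX) |
| Medication side effects | No scheduled instrument described | None | None |

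Section II.B.1 makes between-arm differences in health care utilization a secondary aim and names inpatient admissions. The SAP lists only substance use as secondary, so that aim has no analysis.

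**Step 2. Set the reporting passages side by side.** Read literally, the sentence in Section V.A bars any report of an anticipated event. Appendix C requires serious suicidality to go to a DSMB, and Section VI sends data breaches to a DSMB. Section V gives oversight to the study team and the IRB and sets up no board. These passages cannot all stand as worded.

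**Step 3. Scale.** The plan gives no safety figure to reproduce. The inputs are about 25% with an overdose within 3 years and as many as 50% with self-harm thoughts over six months (both Section V.A), 20 per arm (SAP summary) or 30 per arm (Protocol II.B), and six months of follow-up. Constant hazard is an assumption, as is similarity between the high-risk ED cohort and the trial population.

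- Hazard: −ln(0.75)/3 = 0.0959 per year.
- Six-month risk: 1 − exp(−0.0959 × 0.5) = 1 − 0.75^(1/6) = 4.7%.
- Expected participants with an overdose: 40 × 0.0468 = 1.9, or 60 × 0.0468 = 2.8.
- Chance of at least one: 1 − 0.75^(40/6) = 85%, or 1 − 0.75^(60/6) = 94%.
- If the early hazard were twice the average (assumption): 3.7 of 40 or 5.5 of 60.
- Self-harm thoughts, as a ceiling: 0.5 × 40 = 20, or 0.5 × 60 = 30.

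**Step 4. What an arm with no events would show.** The exact two-sided 95% upper limit is 1 − 0.025^(1/n): 16.8% for n = 20 and 11.6% for n = 30. With the 20% attrition that the protocol expects, 16 or 24 per arm would answer a self-report item, and the limits become 20.6% and 14.2%.

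**Step 5. Would a test help?** Power to detect a doubling of overdose risk (4.7% against 9.4%, two-sided 0.05) is about 8% with 20 per arm and 10% with 30. It would not, so only a descriptive table makes sense.

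**The case against.** A reader might infer from Section V.A that the trial would report its known harms nowhere. The documents do not support that:

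- The sentence stands between the IRB form rule and the notice to the NIDA project officer. It governs what goes to the IRB and says nothing about publication or final results.
- The annual NIDA report carries health care utilization as well as problems reported to the IRB, and admissions are part of utilization.
- Appendix C gives serious suicidality a route to a DSMB.
- Section V.A has safety reports reviewed weekly, although their content is not specified.

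All of this stands. What is missing is a planned summary; the documents contain no rule of suppression.

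There are also fair objections to a simple by-arm count. Intervention activities are one way in which events come to light, and usual care has no equivalent, so log counts would tend to be higher in ED-LINC for the same true rate. Appendix C words item 9a in two ways: one asks about plans over a past period, the other about current thoughts. Attrition of about 20% means that a participant with no recorded event is not necessarily event-free. Side effects have no scheduled instrument. These points shape the table. They do not remove the need for one, because item 9, the overdose self-report and the EDIE data do not depend on intervention contact.

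**Conclusion.** The point holds in this form. The SAP plans no by-arm summary of any anticipated harm and omits utilization, so admissions have no analysis there. Overdoses and side effects that are not unanticipated problems have no stated reporting route. The sentence in Section V.A, the DSMB references in Section VI and Appendix C, and the oversight set up in Section V must be reconciled.

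The events left unsummarised are likely to be real: roughly two or three participants with an overdose, and at most 20 to 30 with self-harm thoughts. The overdose figure rests on the two assumptions in Step 3, and the self-harm figure is a ceiling. Both are shown for 40 and 60 participants because the SAP and the protocol differ. The gap should be closed, but it does not affect the validity of the feasibility outcomes.

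**What to change.** Add a descriptive safety table to the SAP and the final results, by randomised arm and without hypothesis tests.

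1. Lead with sources common to both arms. Give EDIE/EMR admissions, ED visits and recorded deaths over all randomised participants. Give overdose self-report and PHQ-9 item 9 above 0 at each assessment where asked, over those who answered, with that number shown. Attach exact 95% intervals.
2. Show counts from the all-source event log separately, without comparative intervals, and note that intervention contacts give ED-LINC extra chances of detection.
3. List medication side effects as incidental reports, with the assessed relatedness.

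Tabulate item 9a only once its wordings in Appendix C have been reconciled.

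In the protocol, state that the non-reporting sentence in Section V.A concerns IRB reporting only. Reconcile it and the DSMB references with Section V, and add the table to the annual NIDA report in Section IX. The SAP is dated September 2021 and partly written in the past tense. If protocol edits come too late, the table can still go into the SAP and the results.

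The cost is one SAP section, a few protocol sentences and a little analysis of data already collected. The intervals will be wide, and the table will show that openly.
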